9.4.2 Analysis of Secondary Endpoints

Continuous secondary efficacy endpoints with repeated measures will also be analyzed based on data collected during the treatment period, including TLFB and other questionnaire data assessed at Week 13 that reflect data collected during this period.

In general, every continuous secondary efficacy endpoint with repeated measures is analyzed using a repeated measures mixed effects model as discussed in Section 9.4.1. Results will be presented using the same tabular and graphical formats detailed in Section 9.4.1. The primary analysis model is:

appropriately transformed endpoint = treatment + week + treatment*week + clinical site + baseline equivalent of endpoint + other covariates (identified in Section 9.4.3).

It is anticipated that the covariance structure selected for the primary endpoint will also be used for secondary endpoints; however, the selection process detailed in Section 9.4.1 will be followed for each continuous secondary endpoint.

The primary analysis model for continuous endpoints measured at one time is a general linear model (GLM): appropriately transformed endpoint = treatment + clinical site + baseline equivalent of the endpoint + other covariates (identified in Section 9.4.3).

The primary analysis model for dichotomous endpoints is a logistic regression model that includes treatment + clinical site + other covariates (identified in Section 9.4.3). If fewer than 5 events are observed for a dichotomous endpoint then no logistic regression will be performed. In this situation Fisher's exact test will be used to compare treatment groups.

All analyses of secondary endpoints will use the Full Analysis Set.

Descriptive statistics of all secondary endpoints will be reported for all study weeks (1-12) or times at which they were measured within the treatment period, by treatment group.

9.4.2.1 Secondary Drinking Endpoints

The continuous endpoints – percentage of days abstinent per week, weekly mean number of drinks per week, and weekly mean number of drinks per drinking day – will be analyzed using the mixed effects model specified in Section 9.4.2. Covariates for these models will be identified as in Section 9.4.3.

The dichotomous endpoints –percentage of subjects with a WHO 1-level decrease, and WHO 2-level decrease in alcohol consumption risk category, percentage of subjects with no heavy drinking days, and percentage of subjects abstinent from alcohol – will be assessed for the entire 10-week maintenance period, with 1- and 2-month grace periods, and Month 2 and Month 3. These endpoints will be analyzed with the logistic regression model specified in Section 9.4.2. Covariates for these models will be identified as in Section 9.4.3.

9.4.2.2 Alcohol Use and Craving Endpoints

The MINI AUD module is assessed at screening and Week 13. The number of AUD symptoms at Week 13 is a continuous variable and will be modeled using a GLM specified in Section 9.4.2. Covariates for these models will be identified as in Section 9.4.3.

Craving is assessed using the Urge to Drink Scale which is assessed repeatedly during the treatment period. The total score will be analyzed using the mixed effect model approach detailed in Section 9.4.2. Covariates for this model will be identified as in Section 9.4.3.

9.4.2.3 Psychosocial Endpoints

The POMS, ECR-RS, and the three PROMIS scales (including negative alcohol-related consequences, sleep disturbance, and pain interference) are continuous variables assessed repeatedly throughout the treatment period. The POMS includes the overall Total Mood Disturbance and other subscales, and each will be individually analyzed. The ECR-RS is a 36-item questionnaire of which only the first 18-item attachment-related anxiety scale will be assessed and analyzed. The three PROMIS scales employed in this study will be transformed into T-scores prior to analysis. The POMS, ECR-RS and PROMIS scores will be analyzed using the mixed effect model approach detailed in Section 9.4.2. Covariates for these models will be identified as in Section 9.4.3.

9.4.2.4 Nicotine-Related Endpoints

The dichotomous endpoints – abstinence from smoking and abstinence from nicotine use – will be analyzed with the logistic regression model described in Section 9.4.2. Covariates for these models will be identified as in Section 9.4.3.

The mean number of cigarettes smoked in the past week is a continuous variable measured repeatedly during the treatment period. This endpoint will be analyzed only for those subjects who smoked at baseline. The data will be analyzed using the mixed effects described in Section 9.4.2. Covariates for this endpoint will be identified in Section 9.4.3.

The mean numbers of days of other nicotine product use is a continuous variable measured repeatedly during the treatment period. This endpoint will be analyzed only for those subjects who used other nicotine products at baseline. The data will be analyzed as described in Section 9.4.2. Covariates for this endpoint will be identified in Section 9.4.3.

9.4.3 Covariate Adjustment for the Analysis of Endpoints

Covariates for the continuous efficacy endpoints measured repeatedly include the baseline equivalent of the endpoint, clinical site, treatment, time and the treatment by time interaction. Covariates for the continuous efficacy endpoints measured at a single time point include the baseline equivalent of the endpoint, clinical site, and treatment. Covariates for the dichotomous endpoints include treatment and clinical site; however, the number of covariates will depend upon the number of events. In general, 10 events per covariate are necessary for a stable logistic regression model (Peduzzi et al, 1996). If the number of events permits the inclusion of a baseline drinking covariate, the percentage of days abstinent will be used as the covariate for the percent subjects abstinent endpoint; the percentage of heavy drinking days will be used as the covariate for the percent subjects with no heavy drinking days endpoint; however, no baseline drinking covariate will be employed for the endpoint, percent subjects with a WHO decrease in alcohol consumption, as this endpoint already adjusts for baseline drinking in its calculation. If there are only 5-9 events in one of the dichotomous endpoints then a logistic regression will be performed with treatment group as the only covariate.

Clinical site is included as a covariate because it was chosen as a stratification variable to account for between site variability in outcome. Prior to conducting the logistic regression, a blinded analysis of site by treatment group by dichotomous secondary outcome will be performed to determine if every site has an outcome. Clinical sites with fewer than 3 events will be combined for the purpose of conducting the logistic regression. The baseline equivalent of the endpoint is a strong predictor of the endpoint and will generally be included as a covariate.

Additional covariates for the efficacy endpoints may include baseline characteristics with a theoretical and/or empirical basis for a relationship with a particular endpoint. Such characteristics may include, but are not limited to, drinking goal, age, and years of regular drinking (age minus age first started drinking alcohol regularly). Prior to the unblinding of the data, matrices of correlations between these baseline characteristics and each of the secondary efficacy endpoints, pooled across blinded treatment assignment, will be produced (using Pearson for continuous variables, Spearman for categorical outcomes). Selection of baseline variables to include as covariates in the models will be based on consideration of the following criteria: at least modest correlation with outcome (i.e., $r \ge 0.20$), and clinical expertise. Each endpoint may have a unique set of covariates. Care is taken to only select a limited number of covariates such that the models are not over fitted

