3.2 Study Design

This study is a double-blind, randomized, placebo-controlled, parallel group, multi-site clinical trial designed to assess the efficacy of oxytocin compared with placebo to reduce drinking in 100 subjects (50 in each group) who report 4 or more Diagnostic and Statistical Manual of Mental Disorders – Fifth Edition (DSM-5TM) symptoms of AUD. This study will be conducted at 4 clinical sites. If eligible for the study, subjects will be randomized using a stratified permuted block randomization procedure with "clinical site" as a stratification variable in an approximate 1:1 ratio (targeting 50 subjects per group) to receive either intranasal oxytocin or placebo for 12 weeks.

[figure not shown]
If eligible for the study, subjects will receive blinded intranasal oxytocin at 35 IU once per day or intranasal placebo (same volume once per day) for 2 weeks (initial tolerability assessment period), then for the next 10 weeks (maintenance period) subjects will receive oxytocin at 35 IU/twice per day (BID, totally daily dose 70 IU) or intranasal placebo (same volume twice per day)

Subjects will be seen in the clinic at screening visit(s), at randomization, and at Weeks 2, 3, 4, 6, 8, 10, and 13. During the alternate weeks when subjects will not be coming into the clinic (Weeks 5, 7, 9, 11, and 12), subjects will be contacted once during that week by telephone to encourage study drug compliance and to assess withdrawal, adverse events (AEs), and concomitant medication use. A final follow-up telephone interview will occur during Weeks 14/15 (1-to-2 weeks after the end of dosing).

Enrollment will be halted if 2 or more at least possibly related SAEs as judged by the investigator or medical monitor occur. If this occurs, a DSMB meeting will be convened and a decision, in conjunction with the study Sponsor, will be made regarding stopping the study.

The overall study schema is provided in Figure 1. The study schedule of visits and assessments is shown in Table 1.

Figure 1. Overview of Study Design

*Telephone contact, otherwise visit is in clinic

Oxytocin for Alcohol Use Disorder Protocol Number: NCIG-007R

Table 1. Schedule of Assessments

	Screen						ľ	Mainte	nance					EOS ^a	Safety Follow-up
Study Week	-2 to -1	1	2	3	4	5	6	7	8	9	10	11	12	13	14/15
Clinic Visit #	1	2	3	4	5		6		7		8			9	
Informed Consent	X														
Alcohol Breathalyzer	X	X	X	X	X		X		X		X			X	
Urine Drug Screen ^b	X	X	X	X	X		X		X		X			X	
Locator Form	X														

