5.1.5 Weekly Percentage of Heavy Drinking Days and Weekly Percentage of Days Abstinent

Weekly percentage of heavy drinking days is the number of heavy drinking days in a 7-day period divided by 7 then multiplied by 100. The TLFB permits capturing data in a subsequent visit if a visit is missed; however, if fewer than 7 days are observed, then the denominator is the number of days observed in the 7-day period. At least 3 days in a week must be observed; otherwise, the week is considered missing.

Weekly percentage of days abstinent is similarly calculated by using the number of days abstinent instead of the number of heavy drinking days.

5.1.6 Percentage of Subjects with No Heavy Drinking Days and the Percentage of Subjects Abstinent from Alcohol

The percentage of subjects with no heavy drinking days is the number of subjects that have no heavy drinking days during the period of interest divided by the number of subjects with at least one day of non-missing drinking data during the period of interest, multiplied by 100.

The percentage of subjects abstinent from alcohol is calculated similarly, except the numerator is the number of subjects that have no drinking days during the period of interest.

5.1.7 Weekly Mean Number of Drinks and Weekly Mean Number of Drinks per Drinking Day

Weekly mean number of drinks is the sum of SDUs calculated to the tenths over 7 calendar days divided by the number of days with non-missing data. The quotient is multiplied by 7. At least 3 days in a week must be observed; otherwise, the week is considered missing.

Weekly mean number of drinks per drinking days utilizes the same numerator, and the denominator is the number of days with greater than 0 SDUs. Weeks where all days within the week are abstinent are assigned a value of 0 for weekly drinks per drinking day.

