9.0 STATISTICAL CONSIDERATIONS

9.1 General Considerations

For descriptive purposes, dichotomous and categorical variables will be presented as number of observations and percentages; continuous variables will be given as means, standard deviations (SD), median, minimum (min) and maximum (max). Statistical tests will be two-tailed at a 0.05 Type I error rate. P-values for the primary and secondary endpoints of < 0.05 will be considered statistically significant. Endpoint data will also be screened for outliers and skewness. Appropriate non-parametric tests will be used to compare treatment groups on continuous baseline characteristics that are not normally distributed. Continuous endpoint data that are not normally distributed will be transformed using either a square root, logarithmic, or inverse transformation, the selection of which is determined by skewness and kurtosis statistics with values closest to zero and normalization of histograms. Cohen's d will be used to calculate the effect size for means. Odds ratios will be provided for all dichotomous outcomes. Descriptive statistics – mean, SD, median, min and max – of all endpoint data will be provided for each assessment point or summarized at each week for drinking endpoints. All data will be presented in listings. All analyses will be performed in the full analysis set.

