Oxytocin	9	XX.XX	0.xxx	0.xxx	0.xxx	X.XXX	X.XXX	0.xxx	XX.XXX	0.xxx	XX.XXX
Placebo	9	XX.XX	0.xxx	0.xxx	0.xxx						
Oxytocin	10	XX.XX	0.xxx	0.xxx	0.xxx	X.XXX	X.XXX	0.xxx	XX.XXX	0.xxx	XX.XXX
Placebo	10	XX.XX	0.xxx	0.xxx	0.xxx						
Oxytocin	11	XX.XX	0.xxx	0.xxx	0.xxx	X.XXX	X.XXX	0.xxx	XX.XXX	0.xxx	XX.XXX
Placebo	11	XX.XX	0.xxx	0.xxx	0.xxx						
Oxytocin	12	XX.XX	0.xxx	0.xxx	0.xxx	X.XXX	X.XXX	0.xxx	XX.XXX	0.xxx	XX.XXX
Placebo	12	XX.XX	0.xxx	0.xxx	0.xxx						

				95% CI				Untransformed		Transformed	
Arm	Week	Estimate	SE	Lower CI	Upper CI	Difference	SE	p-value	Cohen's d	p-value	Cohen's d
Oxytocin	Overall	xx.xx	0.xxx	0.xxx	0.xxx	x.xxx	X.XXX	0.xxx	XX.XXX	0.xxx	XX.XXX
Placebo	Overall	XX.XX	0.xxx	0.xxx	0.xxx						

¹Values are based on untransformed data unless otherwise specified

Table 28: Drinks per Drinking Day from Baseline to Week 12

Same format as Table 18

Table 29: Drinks per Drinking Day – Mixed Effects, Weeks 3-12

Same format as Table 19

Table 30: Percent Days Abstinent from Baseline to Week 12

Same format as Table 18

Table 31: Percent Days Abstinent – Mixed Effects, Weeks 3-12

Same format as Table 19

Table 32: WHO Shift Baseline to Weeks 3-12

	Week 3-12 Category ^a									
Baseline	Abstinent	Low Risk	Medium Risk	High Risk	Very High Risk					
Category	n (%)	n (%)	n (%)	n (%)	n (%)					
High Risk										
Very High Risk										

^a Percent is based upon row denominator (eg # subjects with High Risk at baseline)

Same table for Oxytocin subjects only

Same table for Placebo subjects only

Table 33: WHO 1-Level Decrease in Alcohol Consumption – Weeks 3-12

	Placebo	Oxytocin	Total
	(N=xx)	(N=xx)	(N=xxx)
WHO 1-Level Decrease			
Yes	xx (xx.x%)	xx (xx.x%)	xx (xx.x%)
No	xx (xx.x%)	xx (xx.x%)	xx (xx.x%)

Table 34: WHO 1-Level Decrease in Alcohol Consumption – Full Model, Logistic Regression, Weeks 3-12

								95%	6 CI
Parameter		DF	Estimate	Standard Error	Wald Chi-Square	Pr > Chi-Square	OR	Upper CI	Lower CI
Intercept		1	XX.XXX	XX.XXX	XX.XXX	0.xxx			
Treatment	Oxytocin	X	XX.XXX	XX.XXX	XX.XXX	0.xxx	XX.XXX	XX.XXX	XX.XXX
Site	Overall	X	XX.XXX	XX.XXX	XX.XXX	0.xxx			
Site	1	X	XX.XXX	XX.XXX	XX.XXX	0.xxx	XX.XXX	XX.XXX	xx.xxx
Site	210	X	XX.XXX	XX.XXX	XX.XXX	0.xxx	XX.XXX	XX.XXX	XX.XXX
Cov		X	XX.XXX	XX.XXX	XX.XXX	0.xxx	XX.XXX	XX.XXX	xx.xxx

Table 35: WHO 1-Level Decrease in Alcohol Consumption – Weeks 9-12 (2 Month Grace)

Same style as Table 33

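### The SAP has no rule for a dichotomous endpoint with 5-9 events when one arm has none: the logistic odds ratio is then infinite and its Wald test uninformative.

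*SAP*

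**What the plan says.** SAP 9.4.2 and 9.4.3 together set out a ladder for dichotomous endpoints, by total number of events.

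- Fewer than 5 events: "If fewer than 5 events are observed for a dichotomous endpoint then no logistic regression will be performed", and Fisher's exact test compares the arms.
- 5 to 9 events: "If there are only 5-9 events in one of the dichotomous endpoints then a logistic regression will be performed". That model contains treatment and nothing else.
- More events: treatment, site and possibly other covariates, guided by the statement "In general, 10 events per covariate are necessary for a stable logistic regression model".

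The only other provision for sparse data concerns sites: "Clinical sites with fewer than 3 events will be combined for the purpose of conducting the logistic regression". Site is not in the 5-9 event model, so this does not help there.

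SAP 9.1 adds: "Odds ratios will be provided for all dichotomous outcomes". The SAP text does not name the test statistic for the logistic model. The shells for the logistic tables (Tables 34, 40, 50 and 86) have a column headed "Wald Chi-Square", next to the odds ratio and its 95% confidence limits. The Figure 4 shell marks significant p-values with a star.

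**The concern.** The switch to Fisher's test depends on the total event count, not on how the events fall between the arms. An endpoint with 6 to 9 events, all in one arm, therefore goes to logistic regression. That model has no finite estimate: the treatment coefficient grows with every iteration, its standard error grows faster, and the Wald p-value drifts towards 1. The test fails exactly where the arms differ most clearly.

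The plan would then deliver neither the promised odds ratio nor a usable p-value. The analyst would have to choose a replacement (likelihood ratio, exact, penalised, Fisher) after seeing the split by arm, and these can give very different p-values.

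**Working it through.** **Inputs.** Arm size: SAP 7.0 projects 100 × (1 − 0.12) = 88 subjects, 44 per arm, for the primary endpoint; the target is 50 per arm. I use both. Tests are two-sided at 0.05 (SAP 9.1). The documents give no event rates for the dichotomous endpoints, so all rates below are assumptions.

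**The plan's own figure.** The only design calculation is the primary-endpoint power. With d = 0.60 and 44 per arm, 0.60 × √(44/2) − 1.96 = 0.854, a power of 0.80 (0.795 with the noncentral t). It reproduces, but this point does not depend on it.

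**Fisher p for e events against none, equal arms of n:** p = 2 × C(n,e) / C(2n,e). For 6-0 at n = 44: 2 × 7,059,052 / 541,931,236 = 0.026.

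| Split | Fisher p, 44 per arm | Fisher p, 50 per arm | Exact lower 95% limit of odds ratio, 44 per arm |
|---|---|---|---|
| 5-0 | 0.055 | 0.056 | |
| 6-0 | 0.026 | 0.027 | 1.26 |
| 7-0 | 0.012 | 0.0125 | 1.57 |
| 8-0 | 0.0055 | 0.0058 | 1.91 |
| 9-0 | 0.0025 | 0.0026 | 2.26 |

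The lower limit is the odds ratio ψ that solves C(44,e)ψ^e / Σ C(44,x)C(44,e−x)ψ^x = 0.025, summing over x = 0 to e.

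**Wald p for the same tables.** Newton-Raphson from zero at 44 per arm gives, after 8, 12 and 20 iterations, p = 0.62, 0.92 and 0.997 for 6-0, and 0.60, 0.92 and 0.997 for 9-0. The likelihood-ratio test for 6-0 gives chi-square 8.76, p = 0.0031. One table thus yields 0.003, 0.026 or 0.6 to 1, depending on a choice the SAP text does not make.

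**Events in both arms.** Here Wald is finite: z = ln(OR) / √(1/a + 1/b + 1/(n−a) + 1/(n−b)). For 8-1 at 44 per arm, OR = (8 × 43)/(1 × 36) = 9.56, SE = 1.084, z = 2.08 and p = 0.037; Fisher gives 0.030. Over every split with 5-9 events at equal arms of 44 or 50, Fisher and Wald disagree at 0.05 only for 6-0, 7-0, 8-0 and 9-0.

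**How often.** Two binomials were enumerated exactly for the chance, per endpoint, of 5-9 events with Fisher p < 0.05 and Wald p ≥ 0.05. The last column uses twice the smaller tail as the two-sided Fisher p; with equal arms the two conventions coincide.

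| Assumed rate, placebo vs oxytocin | 44 vs 44 | 44 vs 43, doubled tail |
|---|---|---|
| 5% vs 5% | 0.5% | 0.4% |
| 10% vs 20% | 0.5% | 0.5% |
| 5% vs 10% | 2.8% | 2.6% |
| 4% vs 12% | 6.7% | 6.4% |
| 3% vs 12% | 10.6% | 10.1% |
| 2% vs 14% | 21.1% | 20.6% |

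The last row assumes an odds ratio of (0.14/0.86)/(0.02/0.98) = 8.0.

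**Unequal arms.** They are to be expected: allocation is "in an approximate 1:1 ratio (targeting 50 subjects per group"), and the denominator for no heavy drinking and for abstinence in SAP 5.1.6 is "the number of subjects with at least one day of non-missing drinking data during the period of interest". Over all 55 arm-size pairs from 40 to 52 differing by at most 4, there are 1650 splits with 5-9 events and events in both arms. Default two-sided Fisher (summing all tables no more probable than the observed one) and Wald disagree at 0.05 in 19 of them; with the doubled tail, in 1.

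**The case against.** A reader might infer that the SAP contradicts its own 10-event rule. It does not. That statement is a general guideline, and the 5-9 tier is an explicit, pre-specified exception in the same paragraph. Where both arms have events, the choice of cut-off makes no difference at 0.05 with equal arms of 44 or 50. What stands is narrower: the exception supplies no rule for an empty arm.

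A reader might also infer that a 9-0 result would be published without a star while 8-1 would carry one. That requires Wald to be the decision test and a non-converged fit to be accepted. Wald is only inferred from shells, mostly for the full model, whose site rows do not match a four-site trial. Counts by arm are tabulated and SAP section 10 requires independent validation, so a divergent fit would probably be noticed. That protects against printing a meaningless p-value. It does not settle which test replaces it, and the choice would come after the split is known.

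Finally, at 44 placebo and 43 oxytocin the default Fisher p raises the largest chance to 33.0%. The rise comes from the convention: with unequal arms, 5-0 becomes significant when the events lie in the smaller arm (p = 0.026 at 43 vs 44), although the exact lower limit is 0.98. With a p-value consistent with the exact interval, the figure is 20.6%. The 33% should not be used as the size of the problem.

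**Conclusion.** The gap is real and limited. At 5-9 events with one empty arm, following the SAP as written gives an infinite odds ratio and, if the shells are followed, an uninformative p-value for splits of 6-0 to 9-0 that Fisher's test finds significant. The documents support neither a charge of self-contradiction nor a claim that logistic regression at 5-9 events misleads when both arms have events.

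Only dichotomous secondary endpoints are affected, and protocol 11.4.11 applies no multiplicity adjustment to these in a trial it describes as a pilot. The primary analysis is untouched. The chance per endpoint of about 0.5% to 21% rests on assumed rates, and its upper end needs a very large effect. Smoking and nicotine abstinence have smaller denominators and are not covered by these figures. The change is worth making because it is cheap and must be fixed before the arm-level split is known.

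**What to change.** Before unblinding, state in SAP 9.4.2 and 9.4.3 that for any dichotomous endpoint with fewer than 10 events in total, or with no events or no non-events in one arm at any event count, the p-value comes from Fisher's exact test and the odds ratio is reported with an exact 95% confidence interval (one bound only if an arm is empty). The second condition is needed because a count threshold alone leaves a 10-0 split (Fisher p = 0.0011 at 44 per arm) without a rule.

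State once, for every use of Fisher's test in the SAP, which two-sided p is meant. Twice the smaller tail agrees with the exact interval when arms are unequal.

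The cost is a sentence in each section, a footnote in the logistic shells and minor programming. Below 10 events no covariate is lost, since the model it replaces contains treatment only; with an empty arm at 10 or more events, the adjustment for site is given up. Fisher's test is slightly conservative, and a few borderline decisions can change with unequal arms: 19 of 1650 splits with the default p, 1 of 1650 with the doubled tail (7-1 at 44 vs 46: 0.0501 against Wald 0.0498).
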